9.5. Study size

The sample size formula follows the binomial approach for binary outcomes where:

$$N^{0.5} = (Z_{1-\alpha} + Z_{1-\beta}) (p(1-p))^{0.5} / M$$

For 90% power, the formula results in 78 individuals for sensitivity and 128 individuals for specificity. Using various keyword search, feasibility assessment was performed. In the Optum EHR data, after applying inclusion and exclusion criteria in [Section 9.2.1](#) and [Section 9.2.2](#), there were 422 potential ATTRwt-CM records available; yet, before reviewing the unstructured notes, one is unable to determine the total number of clinically diagnosed ATTRwt-CM patients. Given that ATTRwt-CM is a rare disease for which the ICD-10 code has only been available recently and the use of which clinicians are still not quite familiar with or comfortable using, the team will attempt to maximize the number of

PFIZER CONFIDENTIAL

potential cases by performing note review for all 422 charts. Similar number of control charts will be reviewed to balance the number of cases and controls. Any increase in sample size will result in more precise 95% CIs.

We estimate that the sample sizes will likely provide 90% power to satisfy the non-inferiority hypotheses listed below.

The non-inferiority hypotheses are:

H0: Sensitivity ≤ 0.80

H1: Sensitivity ≥ 0.90

and

H0: Specificity ≤ 0.72

H1: Specificity ≥ 0.82

Sensitivity and Specificity estimates were evaluated based on the validation and performance metrics from the random forest-based ML risk prediction model receiver operating characteristics curve in Huda et al.¹ Sensitivity is defined as the probability that an individual with the disease in the population will screen positive for disease by the algorithm (True Positives). Specificity is defined as the probability that an individual without the disease will be correctly identified as not having the disease by the algorithm (True Negatives).

The distance from H0 to H1 is the non-inferiority margin (NIM), which is 0.10 for both sensitivity and specificity.

For sensitivity, we wish to reject H0 (inferiority to 0.90) in favor of H1 (non-inferiority to 0.90) while for specificity we wish to reject H0 (inferiority to 0.82) in favor of H1 (non-inferiority to 0.82).

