9.7. Data Analysis

9.7.1. Statistical Methods

The ML model will identify patients with HF as suspected ATTRwt-CM and the remainder patients as not suspected for ATTRwt-CM/non-amyloid HF. The patients with HF will be entered in the ML algorithm along with their diagnosis codes listed in all their records. The model will classify patients based on the presence and absence of cardiomyopathy features and categorized as suspected (at-risk) or not suspected with ATTRwt-CM. The model performance metrics (sensitivity and specificity) will be calculated by cross-tabulating between diagnosis based on ML algorithm and diagnosis based on chart ascertainment.

The analyses for noninferiority of sensitivity and specificity are straightforward. The calculations for these measures are shown below.

PFIZER CONFIDENTIAL

CT24-WI-GL02-RF02 4.0 Non-Interventional Study Protocol Template For Secondary Data Collection Study

01-Jun-2022

Page 19 of 25

Table 1. Sensitivity and Specificity

ML classification	Cohort (Ascertained by Charts)		TP+FP
	ATTRwt-CM	Non-amyloid HF	
+	True Positive (TP)	False Positive (FP)	TP+FP
-	False Negative (FN)	True Negative (TN)	TN+FN
	TP+FN	TN+FP	

Sensitivity = TP / (TP + FN)

Specificity = TN / (TN + FP)

We would then calculate the one-sided 95% confidence interval (CI) for sensitivity, assuming 90% power:

$$95\% \text{ CI} = \text{sensitivity} - 1.645(\text{SE}_{\text{sensitivity}})$$

where $\text{SE}_{\text{sensitivity}} = \text{square root} [\text{sensitivity} - (1-\text{sensitivity})]/n_{\text{sensitivity}}$

The 95% CI for sensitivity must equal or exceed a cut point (CP) value between 0.80 and 0.90 where:

$$\text{CP} = 0.90 - \text{NIM Z1-} \beta / (\text{Z1-}\alpha + \text{Z1-}\beta)$$

When $\alpha = 0.05$ and power = 0.90 we reject inferiority for all values $\geq \text{CP} = 0.8561$.

Similarly, for specificity, we reject inferiority for all values $\geq \text{CP} = 0.7761$.

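### Section 9.7.1 applies a point-estimate cut point to the lower confidence bound, so the rule as written tests against about 0.856/0.776, not the stated 0.80/0.72, and misses the planned 90% power

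*Combined protocol and SAP*

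**What the plan says.** Section 9.5 sets the hypotheses: "H0: Sensitivity ≤ 0.80" against an alternative of 0.90 or more, and "H0: Specificity ≤ 0.72" against an alternative of 0.82 or more, each with a margin of 0.10. It gives the sizes: "For 90% power, the formula results in 78 individuals for sensitivity and 128 individuals for specificity". It plans to review all 422 candidate case charts and a similar number of control charts, and says that the number of confirmed cases is not yet known.

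Section 9.7.1 gives the decision rule. It begins "We would then calculate the one-sided 95% confidence interval (CI) for sensitivity, assuming 90% power" and defines the bound as the estimate minus 1.645 SE. The operative sentence is "The 95% CI for sensitivity must equal or exceed a cut point (CP) value between 0.80 and 0.90". The cut point is CP = 0.90 − NIM × Z(1−β) / (Z(1−α) + Z(1−β)). The section then states that, with alpha 0.05 "and power = 0.90 we reject inferiority for all values" at or above 0.8561. For the other endpoint it says "Similarly, for specificity, we reject inferiority for all values" at or above 0.7761.

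**The concern.** The only sentence that says what is compared with the cut point names the confidence bound. Yet the cut point already contains the 1.645 SE allowance. If both are used, the null actually tested is the cut point, and an algorithm observed exactly at its target fails at the planned sample size.

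The phrase about rejecting for all values at or above the cut point does not say whether the value is the estimate or the bound. The study's only prespecified success criterion can therefore be read in two ways that often give opposite conclusions on the same data. If this is left open, the reading could be chosen after the results are seen.

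**Working it through.** **Inputs.** From section 9.5: nulls 0.80 and 0.72, planning values 0.90 and 0.82, margin 0.10, sizes 78 and 128, 422 candidate case charts. From section 9.7.1: one-sided alpha 0.05, power 0.90, cut points 0.8561 and 0.7761. The normal quantiles are 1.64485 and 1.28155, which sum to 2.92641. The SE is taken as √(p(1−p)/n). The printed SE has a minus sign between its two terms, which may be a text-extraction fault, and nothing here relies on it.

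**1. The plan's own figures.** N = 2.92641² × p(1−p) / 0.10².
- Sensitivity: 8.5638 × 0.09 / 0.01 = 77.07, so 78.
- Specificity: 8.5638 × 0.1476 / 0.01 = 126.40, so 127 (the plan has 128).
- Cut points: 0.90 − 0.10 × 1.28155 / 2.92641 = 0.8562, and 0.7762 for specificity.

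These match the plan up to rounding. The printed and unrounded cut points give the same critical counts at every size shown below.

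**2. What the cut point is.** The two Z fractions sum to 1, so 0.90 − 0.10 × 1.28155/2.92641 = 0.80 + 0.10 × 1.64485/2.92641 = 0.8562. This is the null plus 1.645 SE at the planned size:
- Sensitivity: SE = √(0.09/78) = 0.0340, and 0.8562 − 1.645 × 0.0340 = 0.800.
- Specificity: SE = √(0.1476/128) = 0.0340, and 0.7762 − 1.645 × 0.0340 = 0.720.

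An estimate at the cut point already has its lower bound at the null.

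**3. Results exactly on target fail the literal rule.** An observed 0.90 at n = 78 has bound 0.844, below 0.8561. An observed 0.82 at n = 128 has bound 0.764, below 0.7761.

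**4. Exact binomial power at true 0.90/0.82.** 211 per group is an illustrative assumption (half of 422); 422 is the most the case charts allow.

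| Cases / controls | Literal rule needs | Literal power | Both pass | Point-estimate power | Both pass |
|---|---|---|---|---|---|
| 78 / 128 | 71 / 107 | 47.5% / 37.0% | 17.6% | 91.3% / 89.3% | 81.6% |
| 211 / 211 | 189 / 173 | 63.6% / 54.5% | 34.7% | 98.1% / 95.3% | 93.4% |
| 422 / 422 | 373 / 341 | 88.0% / 76.1% | 67.0% | 99.8% / 98.9% | 98.7% |

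The both-pass columns are products, because cases and controls are different patients. They apply only if success requires both endpoints. Two tests at 90% would give 0.90 × 0.90 = 81%.

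Under the literal rule, 90% power for specificity needs about 656 controls by normal approximation with the printed cut point (659 unrounded). By exact binomial it needs 670 to 704: power first reaches 90% at 670 and stays there from 704.

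**5. Type I error at the stated nulls (exact).**
- Literal rule: 0.7% at 78 cases, 0.16% at 128 controls.
- Point-estimate reading, sensitivity: 12.0% at 78, 1.8% at 200, 0.13% at 422. The fall with n arises because the cut point is fixed. The 12.0% comes mainly from using the variance at 0.90, and from discreteness: the normal approximation gives 4.9% with that variance and 10.7% with the variance at 0.80.
- Point-estimate reading, specificity: 7.2% at 128.

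**6. How often the readings disagree.** They give opposite verdicts at 67–70 of 78 cases and at 100–106 of 128 controls. Any result that passes the literal rule also passes the point-estimate reading, so the disagreement rate is the difference between the both-pass columns:
- 78/128: 0.816 − 0.176 = 0.640
- 211/211: 0.934 − 0.347 = 0.588 (from unrounded powers)
- 422/422: 0.987 − 0.670 = 0.317

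**The case against.** This is probably a drafting slip. The formula is that of a point-estimate critical value, the closing sentence can be read that way, and on that reading power at 78/128 is 91.3%/89.3%, close to what section 9.5 intends. That is plausible, but it does not settle the matter. The explicit sentence applies the cut point to the interval, and on the other reading the interval would play no part in the decision. The fixed cut point would also fail to hold alpha at the realised sample size.

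The 78/128 figures are formula minima, and the plan reviews many more charts. This stands: the shortfall shrinks as more charts are confirmed. At 422 cases the literal power for sensitivity is 88.0% exact, and the normal approximation puts the 90% point near 400. Specificity at 422 controls still has only 76.1%.

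Section 9.5 joins the two hypotheses with an 'and' but gives no explicit rule that both must pass, so the joint figures are conditional on that. The error is conservative and cannot inflate a claim of performance, which also stands.

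Finally, replacing the Wald bound and resizing go beyond the contradiction itself. Comparing the Wald bound with 0.80 and 0.72 would remove the contradiction, and its excess type I error is modest at large n (5.6% and 5.5% at 422). It is 6.9% at 78 cases and 7.2% at 128 controls, and 6.3% at 200 cases. Since the paragraph must be rewritten anyway, an exact or score bound is the better choice.

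**Conclusion.** The concern holds and should be fixed before the analysis. As written, the rule makes about 0.856 and 0.776 the effective nulls, against 0.80 and 0.72 in section 9.5. Exact power at the planning values is 47.5%/37.0% at 78/128 and 88.0%/76.1% at 422/422. Neither endpoint reaches the stated 90% even if every candidate case chart, and as many controls, are confirmed. The alternative reading roughly keeps the power at 78/128 but conflicts with the explicit sentence and does not hold alpha at the realised size. If both endpoints must pass, the two readings reach opposite study conclusions in 64% of studies at 78/128 and 32% at 422/422. These figures assume true values of 0.90 and 0.82, independent patients, and the usual binomial SE. The practical risk depends on the number of confirmed charts, which the plan does not know.

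**What to change.** In section 9.7.1, replace the cut-point rule with: non-inferiority is declared if the one-sided 95% exact (Clopper-Pearson) lower confidence bound, computed at the realised sample size, exceeds 0.80 for sensitivity and 0.72 for specificity. A score bound is an acceptable alternative. State whether both endpoints must pass.

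In section 9.5, write the alternatives as greater than 0.80 and greater than 0.72, and keep 0.90 and 0.82 as planning values for power.

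Disclose the cost. With the exact bound at 78/128 the critical counts are 69 and 101, type I error is 3.6%/4.7%, and power is 74.9%/84.7%. The sizes for 90% power should be restated as 112–124 cases and 152–164 controls (power first reaches 90% at the lower figure and stays there from the upper). The chart plan covers this if at least 124 of 422 candidate case charts (124/422 = 29%) and 164 of about 422 control charts (39%) are confirmed. Power for sensitivity is then 95.6% at 150 cases, and power exceeds 99% on each endpoint at 200 cases and 422 controls.

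The change is one paragraph in section 9.7.1, plus the alternative-hypothesis lines and two sample-size figures in section 9.5.

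### The fixed cut points 0.8561 and 0.7761 do not deliver the stated alpha of 0.05 with 90% power, whether applied to the estimate or to the confidence bound, and the sizes 78 and 128 share the fault

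*Combined protocol and SAP*

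**What the plan says.** Section 9.5 (Study size) sets the hypotheses "H0: Sensitivity ≤ 0.80" against "H1: Sensitivity ≥ 0.90", and "H0: Specificity ≤ 0.72" against "H1: Specificity ≥ 0.82", with a margin of 0.10 for each. Its sample-size formula has a single variance term p(1-p). The stated result is: "For 90% power, the formula results in 78 individuals for sensitivity and 128 individuals for specificity". The section then plans to review all 422 potential case charts and a similar number of control charts. It concedes that before the notes are read "one is unable to determine the total number of clinically diagnosed ATTRwt-CM patients".

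Section 9.7.1 (Statistical Methods) begins the decision rule with: "We would then calculate the one-sided 95% confidence interval (CI) for sensitivity, assuming 90% power". It next requires this interval to reach a cut point, CP = 0.90 - NIM × Z(1-β)/(Z(1-α) + Z(1-β)). It closes by stating that at alpha 0.05 and "power = 0.90 we reject inferiority for all values" at or above 0.8561, and likewise 0.7761 for specificity. That last sentence does not say whether the values meant are point estimates or confidence bounds.

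**The concern.** A 5% critical value for a proportion depends on the number of patients and on the variance at the null value. CP contains neither. By algebra it equals the null value plus 1.645 standard errors only if the standard error uses the target value (0.90 or 0.82) and the sample is exactly the one that the formula returns. The false-positive rate, however, is determined at 0.80 and 0.72, where the variance is larger: 0.16 rather than 0.09 for sensitivity, and 0.2016 rather than 0.1476 for specificity. The number of confirmed cases is also unknown in advance, so a threshold fixed now can fit only one outcome of the chart review.

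This rule is the study's only stated success criterion, and it decides whether the algorithm counts as validated. If its error rates are not those claimed, a declared success or failure cannot be interpreted at the stated level.

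**Working it through.** **Inputs.** One-sided alpha 0.05 (z = 1.645) and power 0.90 (z = 1.2816) from 9.7.1; null values 0.80 and 0.72, targets 0.90 and 0.82, and margin 0.10 from 9.5.

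**The plan's own figures.**
- Size, variance at the target: (1.645 + 1.2816)² × 0.09/0.01 = 77.1, so 78. For specificity, with 0.1476 in place of 0.09, 126.4, so 127. The printed 128 follows if the z values are rounded up to 1.65 and 1.29: 2.94² × 14.76 = 127.6.
- Size, variance at the null: 137.0 and 172.7, so 138 and 173. The target variance was therefore used.
- Cut point: 0.90 - 0.10 × 1.2816/2.9266 = 0.8562, printed as 0.8561. For specificity 0.7762, printed as 0.7761.

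**Where the nominal 5% comes from.** At 78 cases the cut point lies 0.0561/√(0.09/78) = 1.65 target-variance standard errors above 0.80, but only 0.0561/√(0.16/78) = 1.24 null standard errors. The normal approximation then gives a false-positive rate of 10.8% rather than 4.9%.

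**Reading A: point estimate at or above CP (exact binomial).** False-positive rate at true sensitivity 0.80 or true specificity 0.72:

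| Measure | n | Needed to pass | False-positive rate |
|---|---|---|---|
| Sensitivity | 30 | 26 | 25.5% |
| Sensitivity | 50 | 43 | 19.0% |
| Sensitivity | 78 | 67 | 12.0% |
| Sensitivity | 100 | 86 | 8.0% |
| Sensitivity | 150 | 129 | 3.7% |
| Sensitivity | 200 | 172 | 1.8% |
| Sensitivity | 422 | 362 | 0.13% |
| Specificity | 100 | 78 | 10.8% |
| Specificity | 128 | 100 | 7.2% |
| Specificity | 422 | 328 | 0.4% |

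Power at the targets is 91.3% at 78 cases and 89.3% at 128 controls. Because counts are discrete, a few smaller samples dip to 5% or less, but the rate stays there only from 147 cases and from 180 controls. Above those numbers the rule gives power away: with 300 cases and a true sensitivity of 0.86 it passes 61% of the time, against 86% for an exact 5% test.

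**Reading B: one-sided 95% lower bound at or above CP.** The standard error is printed with a minus sign between sensitivity and its complement. I used the product p(1-p).

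| Measure | n | Needed to pass | False-positive rate | Power at target |
|---|---|---|---|---|
| Sensitivity | 78 | 71 | 0.7% | 47.5% |
| Specificity | 128 | 107 | 0.16% | 37.0% |
| Sensitivity | 422 | 373 | below 0.01% | 88.0% |
| Specificity | 422 | 341 | below 0.01% | 76.1% |

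**The sizes.** An exact one-sided 5% test needs 69/78 for sensitivity (false-positive rate 3.6%, power 74.9%) and 101/128 for specificity (4.7%, 84.8%). With the null variance in the alpha term and the target variance in the power term:
- Sensitivity: (1.645 × √0.16 + 1.2816 × √0.09)²/0.01 = 108.7.
- Specificity: (1.645 × √0.2016 + 1.2816 × √0.1476)²/0.01 = 151.5.

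So the approximation gives 109 and 152. Exact power at 109 cases is 87.3%. It first reaches 90% at 112 cases and 152 controls, and stays there from 124 and 164.

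**How many confirmed cases this means.** Of 422 charts, 78 cases is 78/422 = 18% confirmed and 147 is 147/422 = 35%. The documents give no expected confirmation rate.

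**The case against.** The strongest objection is that the inflation belongs to a rule the plan may not intend. The sentence before the cut-point formula compares the interval, not the estimate, with CP, and the closing sentence can be read as continuing that comparison. On that reading the false-positive rate is well below 5%. This stands, and it limits the claim: a reader might infer that the study will pass an inadequate model 12% of the time, and the documents do not support that. The bound reading does not rescue the stated pair, however, because its power is 47.5% at 78 cases and 37.0% at 128 controls. Even if all 422 case charts and 422 controls were confirmed, it would be 88.0% and 76.1%.

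Second, 78 is the formula's minimum, not the planned enrolment. All 422 potential case charts are reviewed, and with 147 or more confirmed cases even the point-estimate rule does not exceed 5%. This also stands. It would go too far to call a small confirmed number likely, or to describe the error as up to five times nominal, which needs only about 30 confirmed cases (7% of 422).

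Third, sizing on the target variance is a common approximation when the analysis uses the observed proportion in the standard error. That is fair. Comparing such a bound directly with 0.80 at 78 cases gives a false-positive rate of 6.9% and power of 84.6%, milder than the figures above. Still, neither number is the one stated.

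**Conclusion.** The concern holds in this form: the stated combination of alpha 0.05 and power 0.90 is met on neither reading of the rule at the sizes given. Applied to the estimate, the cut point roughly keeps the power but not the alpha (12.0% for sensitivity at 78, 7.2% for specificity at 128). Applied to the bound, it keeps the alpha but loses about half the power or more. The numbers given as sufficient for 90% power are too small for a test that holds 5%: about 112 cases and 152 controls are needed, not 78 and 128.

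These results assume independent binomial counts, true values exactly at the null or target, and the product form of the standard error for the bound reading. Which error would occur in practice depends on the unknown confirmed numbers and on the reading chosen. That choice should not be left until the results are known.

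**What to change.** **Section 9.7.1.** Delete the fixed cut points and the sentence that rejects for all values above them. Declare non-inferiority when a one-sided 5% test that holds its level at the achieved number rejects 0.80 for sensitivity and 0.72 for specificity. The exact binomial test, or equivalently its exact lower bound, would serve; other tests that hold 5% are acceptable. The simple normal-approximation bound should not be used by default, since against 0.80 at 78 cases and 0.72 at 128 controls its false-positive rate is 6.9% and 7.2%. Give example critical counts, such as 69/78, 87/100 and 170/200 for sensitivity and 101/128 for specificity.

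**Section 9.5.** Use the null variance in the alpha term and the target variance in the power term. Restate the minimum confirmed numbers for 90% power as about 112 cases and 152 controls, noting that exact power stays at or above 90% from 124 and 164.

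**Cost.** Protocol wording and two recomputed planning figures. No charts are added, because all 422 are reviewed anyway. The downside is that the stated minimums rise and, compared with a point-estimate rule, a pass is harder when few cases are confirmed.

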9.8. Quality Control

All codes and/or code algorithms will be reviewed by the clinical lead from Pfizer, as well as the protocol authors. The study team will be responsible for upholding high levels of quality control throughout the data analysis and reporting processes. Quality control (QC) checks will be performed on all Python programming, data tables, and reports generated in the course of this research. QC findings and documentation of remedial action will be maintained. Storage of programming, data, and reports will be carried out per standard procedures.

In the validation study, after the Optum NLP team creates key term tags for use in the snippet review for the two Optum clinicians who will review patient notes with these key terms mentioned, the two clinicians will record their findings from the notes regarding whether the notes support a ATTRwt-CM or non-amyloid HF. These results will be provided to the Pfizer study team for review and any clarifications or questions will be managed between the two groups until resolved.

PFIZER CONFIDENTIAL

CT24-WI-GL02-RF02 4.0 Non-Interventional Study Protocol Template For Secondary Data Collection Study

01-Jun-2022

Page 20 of 25

9.9. Limitations of the Research Methods

There are some important limitations to consider for this study:

- Patients may have received health care outside of the network of providers and healthcare organizations that contribute to the Optum databases, or prior to having the index diagnosis and we may not be able to exclude the possibility that a patient was diagnosed with HF, as well as other risk factors, prior to entry into a healthcare system where Optum has EHR access.
- This study utilizes EHR data that have inherent limitations such as the possibility for entry errors and missing information which could lead to extreme or incorrect values. As a result, there is a potential for bias due to a lack of quality control and consistency for data collection and reporting within the database. Study samples obtained from EHR data analyses are not randomly selected and unobserved factors may introduce bias in subject selection.

